## **1.0 OBJECTIVES**

### **1.1 Primary Objective**

- 1.1.1 To determine if patients with locally advanced cervical cancer have longer overall survivals with pretherapeutic paraaortic surgical staging followed by tailored chemoradiation when compared to patients who undergo standard radiologic staging followed by whole pelvic chemoradiation therapy.

### **1.2 Secondary Objectives**

- 1.2.1 To determine if patients with locally advanced cervical cancer have longer disease-free survival with pretherapeutic paraaortic surgical staging when compared to radiologic staging.
- 1.2.2 To determine short- and long-term morbidity of pretherapeutic surgical staging in patients with locally advanced cervical cancer
- 1.2.3 To determine sensitivity of pretreatment staging radiologic examinations in detecting metastatic disease.
- 1.2.4 To determine site of paraaortic metastatic disease along aorta as related to the inferior mesenteric artery (i.e. above or below) in patients with locally advanced cervical cancer
- 1.2.5 To evaluate surgical complication rates of the laparoscopic extraperitoneal paraaortic lymphadenectomy in a large cohort of patients.

## **2.0 BACKGROUND**

According to the International Federation of Gynecology and Obstetrics (FIGO), cancer of the uterine cervix remains a clinically staged disease. Although tumor stage can only be assigned using clinical examination, cystoscopy, proctoscopy, chest X-ray, and intravenous pyleogram, many gynecologic oncologists use more advanced technology for more thorough assessment and treatment planning.

It is not uncommon for patients to undergo computed tomography (CT) scan, magnetic resonance imaging (MRI), and/or positron emission tomography (PET) in the work-up of their disease. Clinicians may glean important information from these tests. First, the presence of positive paraaortic lymph nodes remains the most important prognostic factor for survival in patients with cervical cancer [1,2]. In addition, presence or absence of metastatic disease to the lymph nodes guides treatment planning. This includes the choice of primary surgery or radiotherapy as well as definition of the radiation fields used.

Unfortunately, none of the imaging modalities currently available has proven to be very sensitive in detecting metastatic paraaortic lymph nodes in patients with locally advanced cervical cancer (stages IB2-IVA). CT scan provides a sensitivity of only 67% [4]. While MRI may be beneficial at detecting parametrial, bladder, or rectal invasion from the primary lesions, it is poor at detecting lymph node metastasis. In a meta analysis of MRI and lymph node metastasis, Scheidler et al. [5] reported an overall sensitivity of MRI in detecting lymph node metastasis of 38%. Other authors have found a sensitivity of 0% for the MRI detection of positive paraaortic lymph nodes when compared to the surgical gold standard [6].

Currently, FDG-PET scanning is being utilized in attempts to better detect paraaortic lymph node spread. When combining four prospective studies that compared FDG-PET to gold standard surgical staging, Havrilesky et al. [7] found an overall sensitivity of 84% (95% CI 68-94%). Although this modality is an improvement over CT scan, it remains that 16% (and as high as 32%) of patients will be classified as node negative when in reality they have metastatic disease to their para-lymph nodes. The implications of undertreating these patients are disastrous, especially when one considers that the survival for patients with histologically positive paraaortic lymph nodes is as high as 50% if these metastases are detected and extended field radiation therapy is given [3,8].

The concept of surgical staging for patients with locally advanced cervical cancer has evolved over the last three decades. Surgical staging as a method of assessing lymph node status in patients with locally advanced cervical cancer may lead to a change in the radiation treatment plan in as many as 43% of patients [3]. Initially, patients were staged with traditional laparotomy and a transperitoneal approach. However, this led to a high complication rate from radiation effects on small bowel adhered to dissected areas in the pelvis. The description of the open extraperitoneal approach by Berman et al. [9] led to a sharp decrease in small bowel complications from radiation therapy [10]. Advances in endoscopic equipment and techniques have allowed for even less invasive approaches to lymph node dissection with laparoscopy either transperitoneally [6,11] or extraperitoneally [12-14]. Neither of these approaches appears to increase postoperative radiotherapy complications when surgeries are limited to lymph node dissection only. These procedures do not significantly delay definitive therapy as patients typically go on to receive their radiotherapy 7-10 days following laparoscopic staging.

We recently presented the results of a phase II study of pretherapeutic extraperitoneal paraaortic lymphadenectomy. This study, performed at MD Anderson Cancer Center (MD Anderson), enrolled 65 women with locally advanced cervical cancer. All patients had stage IB2-IVA cervical cancer and underwent PET/CT scan followed by surgical staging via removal of the paraaortic nodes utilizing the laparoscopic extraperitoneal approach. This technique was safe and feasible and did not delay initiation of definitive chemoradiation therapy (median enrollment to treatment time: 10 days). This is not longer than what we would expect for typical time it would take for a patient with newly diagnosed cervical cancer to undergo radiation simulation and treatment planning. Importantly, in women with PET scans showing radiologically positive pelvic nodal metastasis and negative paraaortic metastasis, 22% were found to have pathologically positive metastases after surgical removal. Had treatment planning been based

solely on best available imaging (PET scan), a significant number of women would have received pelvic radiation only and been completely undertreated.

In addition to the prognostic and therapy-directing factors obtained from lymph node dissection, recent data points to a therapeutic benefit of pre-radiotherapy lymph node dissection. Marnitz et al. [11] reported their experience with laparoscopic transperitoneal surgical staging in 84 patients with clinically advanced cervical cancer. They found that patients with microscopically-positive paraaortic lymph nodes that were resected laparoscopically had the same survival as those patients with pathologically negative lymph nodes on surgical staging. LeBlanc et al. [13] also have published their data surgical staging via a laparoscopic extraperitoneal approach in 156 patients with locally advanced cervical cancer. They too found that patients with microscopically-positive and resected paraaortic lymph nodes who then received tailored extended field radiotherapy had the same survival as patients with negative lymph nodes who received pelvic irradiation.

A recent review of three phase III chemoradiation studies by the Gynecologic Oncology Group also showed a survival advantage for women who underwent surgical staging when compared to those who were treated on radiologic findings alone [15]. On multivariate analysis, the relative risk of death for women staged radiologically was 1.46 when compared to women who had surgical staging ( $p=0.43$ ). For women with stage III/IV disease, surgical staging had an even bigger impact with surgically staged women having a 4 year overall survival of 54.3% compared to 40% for those who did not have surgical staging (RR 1.60,  $p=0.038$ ). Whether the survival benefit of surgical staging women with locally advanced cervical cancer is a result of tumor debulking, tailored radiotherapy, or a combination of the two is unknown. Regardless, these important findings should be explored prospectively.

### **3.0 PATIENT ELIGIBILITY**

#### **3.1 Inclusion Criteria**

- 3.1.1 Women with clinical stage IB2-IVA cervical squamous cell carcinoma, adenosquamous, or adenocarcinoma
- 3.1.2 Women with FDG-PET positive or indeterminate pelvic lymph nodes or indeterminate low common iliac nodes (See addendum) and negative paraaortic nodes
- 3.1.3 Women with planned treatment of primary definitive chemoradiation therapy
- 3.1.4 4) An approved Informed consent and authorization permitting release of personal health information must be signed by the patient or guardian.

[figure not shown]
#### **3.2 Exclusion Criteria**

- 3.2.1 Women with stage IA or IB1 cancer
- 3.2.2 Women with prior radiotherapy to the pelvis or retroperitoneal surgery
- 3.2.3 Women with neuroendocrine histologies, or histologies other than squamous, adenosquamous or adenocarcinoma

- 3.2.4 Women with FDG PET positive high common or paraaortic lymph node metastasis confirmed by biopsy (please see addendum).
- 3.2.5 Women who have undergone simple or radical hysterectomy prior to radiotherapy
- 3.2.6 Women with planned treatment of radiotherapy only (without chemotherapy)
- 3.2.7 Women with planned treatment of palliative radiotherapy
- 3.2.8 Women with metastatic disease outside of pelvis.
- 3.2.9 Women who have completed treatment for other malignancies (except non-melanomatous skin cancer) < 5 years from their new diagnosis of cervical cancer
- 3.2.10 Women who are pregnant

#### **4.0 THERAPEUTIC PROGRAM**

This Phase III randomized study is designed to determine if patients with locally advanced cervical cancer have longer overall survivals with pretherapeutic paraaortic surgical staging when compared to radiologic staging.

All eligible patients in MD Anderson and Lyndon B. Johnson General Hospital (LBJ) will be required to sign an informed consent prior to randomization. Patients will be equally allocated between the 2 treatment groups.

Eligible patients will be randomized to either standard chemoradiation (standard-of-care arm) or pretherapeutic paraaortic lymphadenectomy followed by tailored chemoradiation (experimental arm). Pretherapeutic lymphadenectomy will be performed via the laparoscopic extraperitoneal approach using either traditional laparoscopy or robotically-assisted laparoscopy. Patient demographic and treatment information will be collected at time of enrollment and throughout initial definitive therapy (Appendix C).

*Radiology Protocol and Definitions of Positive and Indeterminate Nodes*

All scans will be performed on a dedicated Positron Emission Tomography/Computed Tomography (PET/CT) scanner that will allow fusion of PET and CT images. Standard imaging protocols for PET/CT will be followed with non-contrast CT used for attenuation correction.

The standard definition of abnormal lymph nodes in the abdomen and pelvis by cross sectional imaging is size greater than 10 mm. Therefore nodes greater than 10 mm in the abdomen or pelvis will be considered abnormal by CT.

PET/CT images will be evaluated qualitatively for focal areas of abnormally increased 18-fluorine fluorodeoxy glucose (FDG) uptake. A positive finding is defined as the presence of abnormal FDG uptake when accumulation of the tracer is moderately to markedly increased relative to the uptake in comparable normal structures or surrounding tissues, with the exclusion of physiologic bowel and urinary activity. A negative finding is defined as no detectable FDG uptake.

The FDG PET and PET/CT: EANM procedure guidelines for tumor PET imaging: version 1.0 (Appendix D) states that “it is impossible to give universal rules for [quantitative] detection limits” for what should be considered a positive node of PET scan. It goes on to say “detection limits obviously depend on the degree of contrast between the tumor and its immediate surroundings. Sensitivity of FDG PET is much lower in diabetic patients. There is no single detection limit for FDG PET since it depends on many factors. The most significant of these are: histology (FDG avidity of the type of tumor), the volume of vital tumor cells, movement during acquisition (e.g. blurred signals in the case of pulmonary foci), and physiological uptake in the adjacent background.” Therefore pelvic or paraaortic nodes that are focally more avid than background will be considered positive. Nodes with no detectable FDG uptake above background activity will be considered negative. Indeterminate nodes on CT which are non FDG avid should be followed with the follow up CT to determine stability. If further enlargement is noted, then biopsy may be considered if clinically indicated.

#### *Pretherapeutic Paraaortic Lymphadenectomy:*

Pretherapeutic paraaortic lymphadenectomy should be performed no later than 3 weeks after the PET/CT scan.

The staging surgery begins with a transumbilical diagnostic laparoscopy to assess the peritoneal cavity. If there is no evidence of intraperitoneal disease, an extraperitoneal paraaortic lymphadenectomy is performed through the left sided extraperitoneal approach. Lymph node bearing tissue from the aorta, aortocaval space, vena cava and bilateral common iliac vessels is completely removed from the left renal vein cranially to both common iliac artery bifurcations caudally, and to both psoas muscles laterally. This procedure may be completed via traditional laparoscopy or robotically assisted laparoscopy. If the surgeon encounters perforation of the peritoneum, an additional trocar may be added and a laparoscopic fan placed to attempt to elevate the peritoneum. If it is felt by the surgeon that the laparoscopic retroperitoneal approach is not feasible, a laparoscopic transperitoneal approach may be attempted to complete the procedure. If laparoscopic transperitoneal approach is not successful, the patient may undergo

an open retroperitoneal dissection, an open transperitoneal dissection, or discontinuation of the staging procedure at the surgeon's discretion.

Upon completion of the procedure, clips are placed on the inferior and superior borders of the dissection to guide radiation therapy treatment planning. All specimens are removed in endoscopic bags. If pathologically confirmed fixed or enlarged ( $> 2$  cm) lymph nodes are encountered, attempts will be made to debulk them laparoscopically. Failing this, either clips will be applied to demarcate the area for boost of radiotherapy or the procedure will be converted to an extraperitoneal laparotomy with open debulking. Similarly, although a pelvic node dissection is not part of the procedure as they are already in the radiation field, an open extraperitoneal debulking will be considered to debulk isolated enlarged pelvic nodes at the surgeon's discretion. To avoid the development of postoperative symptomatic retroperitoneal lymphocysts, we will create a transperitoneal opening of the left paracolic gutter to allow the abdominal reabsorption of the retroperitoneal lymph. This step is called "preventive marsupialization." Preventive marsupialization will not be done if a grossly positive node is encountered, resected and the rest of the paraaortic node dissection is abandoned.

In an effort to determine site of metastasis, nodal specimens removed from the inferior mesenteric artery to the renal vessels and labeled "supramesenteric lymph nodes" while nodal specimens removed from the inferior mesenteric artery to the bifurcation of the great vessels will be labeled "inframesenteric lymph nodes."

Pathologic Processing of Lymph Nodes:

The lymph nodes will be serially sectioned perpendicular to the long axis at 2 mm intervals in a "bread loaf" fashion. Lymph nodes 0.5 cm and smaller may be bisected; the node, if bisected, should be cut from hilum to periphery if possible. The lymph node blocks will be submitted for routine sections (1 slide per block).

Radiation Treatment Plan:

For women in the experimental arm, further management of the primary cervical cancer will be tailored to the results of the pretherapeutic staging procedure. Patients with negative paraaortic lymph nodes will be managed with external beam radiotherapy to the pelvis (as defined by the surgical clips applied at the lower limit of the paraaortic node dissection) at a usual dose of 45 Gy. Limited boosts will be indicated individually on clinically involved parametria or pelvic nodes. The external beam radiation therapy will be followed by intracavitary brachytherapy (HDR, LDR or PDR) with intent to cure. Patients with metastatic disease to paraaortic lymph nodes will receive extended-field external beam radiotherapy followed by intracavitary brachytherapy with intent to cure. Patients who complete both external beam radiation and intracavitary radiotherapy will receive a total dose of 80–90 Gy low-dose equivalent to Point A. Concurrent platinum-based chemotherapy will be given with definitive radiation therapy. Chemotherapy will be administered according to each participating institution's standard practice. Patients with carcinomatosis will be given platinum-based chemotherapy along with palliative radiotherapy if indicated.

For women in the standard of care arm, patients with negative paraaortic lymph nodes on PET imaging will be managed with external beam radiotherapy to the pelvis at a usual dose of 45 Gy. Limited boosts will be indicated individually on clinically involved parametria or pelvic nodes. The external beam radiation therapy will be followed by intracavitary brachytherapy with intent to cure (HDR, LDR or PDR). Patients who complete both external beam radiation and intracavitary radiotherapy will receive a total dose of 80–90 Gy low-dose equivalent to Point A. Concurrent platinum-based chemotherapy will be given with definitive radiation therapy.

IMRT may be used for the treatment of the paraaortic nodes. The nodal PTV will receive either 45 Gy in 25 fractions or 50.4 Gy in 28 fractions. Treatment will be delivered once daily, 5 fractions per week, over 5 to 5.5 weeks. Breaks in treatment should be minimized. Positive nodes may be boosted to 60-66 Gy after the initial treatment with IMRT or 3-D conformal treatment at 1.8 Gy or 2.0 Gy per fraction. The dose is prescribed to cover 97% nodal PTV. A volume of at least 0.03 cc within any PTV should not receive > 110% of the prescribed dose. No volume within the PTV that is 0.03 cc or larger can receive a dose that is < 93% of its prescribed dose. Any contiguous volume of 0.03 cc or larger of the tissue outside the PTVs must not receive > 110% of the dose prescribed to the composite PTV

Megavoltage equipment capable of delivering static intensity modulation with a multileaf collimator or dynamic intensity modulation (using a multileaf collimator or tomotherapy) is required. The use of custom made compensators or partial transmission blocks are also acceptable as long as dose specifications and constraints are satisfied. A megavoltage beam of 6 MV or greater must be used, with a minimum source-axis distance of 100 cm. The exception is the use of the Tomotherapy unit that uses 80 cm.

Patients will be immobilized in the supine position in an immobilization device. Patients should, at least, be immobilized in a cradle that fixes the position of the upper body, trunk and proximal legs. Patients will be treated in the immobilization device. Treatment planning CT scans will be required to define tumor, clinical and planning target volumes. The treatment planning CT scan should be acquired with the patient in the same position and immobilization device as for treatment IV contrast may be used during simulation to help better define the vessels; however, it is not required. Oral or rectal contrast is not allowed, because it will interfere with the planning process and may possibly cause anatomical distortion. Contrast may be used during simulation to help better define the vessels; however, it is not required. Oral or rectal contrast is not allowed, because it will interfere with the planning process and may possibly cause anatomical distortion.

If the paraaortic nodes for patients with positive common iliacs are treated, then PTV must end at the top of L2; for patients with positive paraaortic nodes, the PTV must end at the top of T12 (therefore, the CTV must end several slices below these endpoints). The top of the field should be at least one vertebra above the highest positive node. Bowel – will be outlined on every slice, including up to 2 cm above the planning target volume and no more. It includes the volume surrounding loops of small bowel out to the edge of the peritoneum because the bowel may lie within this space at any time throughout the course of treatment.

The dose constraints for critical structures are as follows:

- Bowel:  $\leq 30\%$  to receive  $> 40$  Gy
- Rectum:  $\leq 60\%$  to receive  $> 45$  Gy
- Bladder:  $\leq 35\%$  to receive  $> 45$  Gy
- Kidneys: 2/3 of each kidney to receive  $\leq 18$  Gy
- Spinal cord: no more than 45 Gy at any point with a volume of 0.03 cc or greater

*Follow-Up/Surveillance:*

A PET scan will be obtained at 3 months after completion of chemoradiation therapy. CT scans will be obtained every 6 months for the next three years thereafter. Follow-up surveillance of patients will consist of serial clinical examinations by an oncologist every 3 months for the first 2 years, every 6 months for the next 3 years and annually thereafter. Patients will come off study at 5 years after completion of initial chemoradiation therapy or at time of death.

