## 5.0 STATISTICAL CONSIDERATIONS

### Sample Size Estimation

Based on data collected in the recently completed phase II study at MD Anderson which enrolled 65 women (60 evaluable) with locally advanced, approximately 32% will have PET imaging showing tumor metastasis to the pelvic nodes with negative paraaortic lymph nodes. Of these women, approximately 79% will truly have negative paraaortic lymph nodes. For them, 3 year overall survival with whole pelvis radiotherapy and concurrent chemotherapy is 75%. For the approximately 21% of women with false negative imaging (i.e. pathologically positive paraaortic lymph nodes with negative imaging), the 3 year overall survival with whole pelvis radiotherapy and concurrent chemotherapy is only 10%. If these metastases were known, however, and the radiation field was extended to cover the paraaortic basins, the 3 year overall survival improves to 50%. Thus, the expected overall survival without surgical staging would be approximately 61% and with preoperative paraaortic surgical evaluation would be 70%.

Assuming an accrual rate of 10 patients per month a sample size of 600 patients will yield 80% power with a 2-sided 0.05 significance level to detect a difference in 3-year overall survival of 61% and 70% between the patients without preoperative paraaortic surgical staging and the patients with preoperative paraaortic surgical staging. Accrual would take 5 years, and the study would be expected to take 7.6 years to complete, with a maximum 348 expected deaths. The accrual at LBJ will be 15 patients.

This sample size calculation includes an interim analysis for efficacy and futility once 174 deaths have been observed. The nominal p-value for the interim analysis of efficacy is 0.0031 and the nominal p-value for the interim analysis for futility is 0.3217. The nominal p-value for the final analysis is 0.049. The spending function approach of Lan and DeMets [16] with an O'Brien-Fleming [17] boundary for the interim analysis of efficacy and a Pocock [18] boundary for the interim analysis of futility were used in the sample size estimation. East 5.0 (Copyright © 2007, Cytel Inc., Cambridge, MA) was used to estimate the sample size and plan the interim analyses.

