### Analysis

We will use descriptive statistics to summarize patient demographic and clinical characteristics by treatment group.

We will estimate overall survival (OS) with the product limit estimator of Kaplan and Meier [19], and we will estimate the 3-year OS with a 95% confidence interval. We will also estimate the median OS with a 95% confidence interval. We will use the log-rank test to compare the 2 treatment groups with respect to OS.

We will also use the log-rank test for the interim analysis of OS, which will take place after 131 deaths have been observed. If the p-value from this test is  $< 0.0031$  the study will be stopped for efficacy, and if the p-value from this test is  $> 0.3217$  the study will be stopped for futility.

We will use Cox [20] proportional hazards regression to model OS as a function of treatment and other well-known and potential prognostic factors such as clinical stage, histology, and grade. We will estimate the hazard ratio for treatment (preoperative paraaortic surgical staging vs not) and other potential prognostic factors with 95% confidence intervals.

We will perform similar analyses for disease-free survival (DFS) as for OS.

We will tabulate the numbers of patients with particular short- and long-term morbidities including intraoperative and postoperative complications and treatment delay for each treatment group, and we will use the chi-square test to compare treatment groups with respect to the incidence of these morbidities.

For the treatment arm with pretreatment paraaortic surgical staging we will estimate the sensitivity of pretreatment radiologic staging examinations to detect metastatic disease with a 95% confidence interval. The findings of the pretreatment paraaortic surgical staging will be considered the true diagnosis of metastatic disease.

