## **8.0 PATIENT WITHDRAWAL**

Patients will be advised that they may voluntarily withdraw from the study at anytime, for any reason and it will not affect their medical care. However, in such cases, appropriate effort will be made by the Investigator to determine the reason for voluntary withdrawal from the study and to document reason for withdrawal in the medical record, if known.

The last known status of these patients will be reported with the study results and all attempts to locate patients lost to follow up will also be documented.

Patients will be informed that, should they withdraw from the study, they should remain under the care of an appropriately experienced physician until the physician deems further follow-up unnecessary.

The following are circumstances for which a patient would be identified as not continuing her participation in the study:

- Study Completed / Terminated
- Death
- Voluntary Withdrawal
- Unable to Return
- Physician discretion
- No recurrence of cervical cancer at 5 years after completion of initial chemoradiation therapy
- Failure to complete treatment due to toxicity

If a patient relocates to another geographic area, which requires a change of physician, reasonable attempts will be made to locate and request cooperation from that physician in order to complete follow-up.

In many instances patient withdrawal from the study constitutes a cessation of treatment. In these cases, permission should be obtained from patients by study staff to continue monitoring their disease state (relapse, survival, toxicity etc) via patient records as this is a crucial component of the study for which consent was originally obtained.

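### The 348 deaths behind the 80% power are not expected under the 5-year off-study rule, and no trigger for the final analysis is stated

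*Combined protocol and SAP*

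**What the plan says.** **Section 5.0, Sample Size Estimation.** The plan states that "a sample size of 600 patients will yield 80% power with a 2-sided 0.05 significance level" for 3-year overall survival (OS) of 61% versus 70%. Accrual is 10 patients per month over 5 years, and "the study would be expected to take 7.6 years to complete, with a maximum 348 expected deaths". One interim analysis is planned at 174 deaths, with nominal p-values of 0.0031 for efficacy and 0.3217 for futility. "The nominal p-value for the final analysis is 0.049".

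**Section 5.0, Analysis.** "We will use the log-rank test to compare the 2 treatment groups with respect to OS". A death count is attached to the interim look only (131 here, against 174 in the sample-size text). Neither part of section 5.0 gives a death count or date at which the final test is done.

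**Section 4.0, Follow-Up/Surveillance.** Clinical examinations run every 3 months for 2 years, then "every 6 months for the next 3 years and annually thereafter". The next sentence reads "Patients will come off study at 5 years after completion of initial chemoradiation therapy or at time of death".

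**Section 8.0, Patient Withdrawal.** The reasons for leaving the study include "No recurrence of cervical cancer at 5 years after completion of initial chemoradiation therapy". For withdrawals that mean stopping treatment, staff should ask permission "to continue monitoring their disease state (relapse, survival, toxicity etc) via patient records".

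**The concern.** A log-rank test draws its power from deaths. If every patient leaves at a fixed time, expected deaths level off, and waiting longer adds none. The question is whether 348 deaths can be expected under the plan's own follow-up rule and, if not, what starts the final analysis.

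The follow-up rules also pull in different directions. Section 4.0 schedules annual examinations after year 5 and then takes everyone off study at 5 years after chemoradiation. Section 8.0 names only recurrence-free patients as leaving then. Read literally, section 8.0 would keep relapsed patients at risk while censoring those without recurrence. Censoring after year 5 would then depend on prognosis and distort the late part of the OS curve, though not the 3-year estimate.

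At stake are the stated power and the timing of the primary test. With no trigger written down, that date must be settled after outcome data have started to accumulate.

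**Working it through.** **Inputs from section 5.0.** 600 patients, accrued over 5 years; 3-year OS 61% and 70%; interim at 174 deaths; nominal two-sided p-values 0.0031, 0.3217 and 0.049. Allocation is 1:1 (sections 4.0 and 6.0).

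**Assumptions.** Exponential survival in each arm, uniform accrual, no loss to follow-up, and futility applied as a firm stop, as the Analysis text words it. The lag from randomisation to the end of chemoradiation is not stated; it is taken as 0, 0.25 or 0.5 year, so patients leave at c = 5.0, 5.25 or 5.5 years from randomisation.

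**1. Reproduce the plan's figures (no follow-up limit).**

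- HR = ln 0.70 / ln 0.61 = 0.722, so |ln HR| = 0.326.
- The interim and final Z statistics are bivariate normal, with mean 0.5 × |ln HR| × √deaths and correlation √(174/final deaths). At 174 and 348 deaths the means are 2.15 and 3.04.
- Critical values are 2.958 (efficacy) and 0.991 (futility). Interim stopping probabilities under the planned effect are 0.210 and 0.122, together 0.332. Overall power at 348 deaths is **80.4%**.
- 174 deaths are expected at 5.08 years and 348 at 8.83 years. Averaged over early stopping: 0.332 × 5.08 + 0.668 × 8.83 = **7.59 years**.

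The stated 80% and 7.6 years both reproduce. The 7.6 years is an average duration, not the time at which 348 deaths are reached, and the 348 deaths assume follow-up without a limit.

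**2. Apply the 5-year rule of section 4.0.** Once every patient has reached the limit, expected deaths are

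300 × (1 − 0.61^(c/3)) + 300 × (1 − 0.70^(c/3)).

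| c (years) | Deaths by arm | Total | Chance of 348 | Power |
|---|---|---|---|---|
| 5.0 | 168.4 + 134.4 | 303 | about 0.01% | 77.2% |
| 5.25 | 173.7 + 139.3 | 313 | about 0.2% | 78.0% |
| 5.5 | 178.8 + 144.0 | 323 | about 2% | 78.7% |

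The chance of 348 uses a standard deviation of about 12.2 deaths. Simulation with the limit applied (6,000 trials per limit) gives power of 77.2%, 78.4% and 79.2%. Reaching 348 expected deaths would need c = 6.19 years for every patient.

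**3. Timing.** The 303 to 323 deaths are complete only at about 10.0 to 10.5 years from first randomisation. With the limit, a cut-off at 8.8 years gives 297 to 311 deaths (power 76.6% to 77.8%).

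**4. Sensitivity.**

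- An assumed 2% annual loss to follow-up gives 290 to 308 deaths and 76.0% to 77.6% power.
- These are expectations, not ceilings: 337 to 358 deaths if both arms had 61%, and 269 to 288 if both had 70%.
- Section 5.0 builds 61% and 70% from a node-status mixture (79% of patients at 75%; 21% at 10% or 50%). With exponential survival within each subgroup, expected deaths are lower, at 285 to 302.

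**5. Type I error.** Keeping 0.049 at 303 to 323 deaths gives 0.0497 to 0.0499 two-sided, leaving the futility stop out of the calculation. The level that spends the full 0.05 is 0.0491 to 0.0493.

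**The case against.** The strongest reply is that little power is lost and the text can be read kindly.

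- **Size.** The loss is 1.7 to 3.2 points by calculation, and no bias in the log-rank test is shown under section 4.0's rule. This stands. It also depends on the futility stop: without it, 303 deaths would give 80.9% and 323 would give 83.3%. But the Analysis text words futility as a firm stop, and the plan's own 80% at 348 deaths reproduces only with it (86.0% without).
- **Lag of zero.** Section 4.0 gives 5 to 5.5 weeks of external beam followed by brachytherapy, so 303 is a floor that will not occur. This is fair, but a lag of 0.1 year still gives 307 deaths and 77.5% power.
- **Meaning of off study.** It might mean only the end of protocol visits, since annual examinations are scheduled afterwards and section 8.0 values record-based survival data. That reading is possible, but section 8.0 writes the record monitoring for withdrawals and does not extend it to patients who complete 5 years. If relapsed patients stayed on, more deaths would be counted; the documents give no recurrence rate from which to compute how many.
- **Conflict overstated.** Section 8.0 also lists study completion, which could cover relapsed patients at 5 years. Prognosis-dependent censoring follows only from the literal reading. That is a reason to clarify the wording.
- **Implied trigger.** An interim at exactly half of 348 suggests a final look at 348. If so, the trigger is one that the 5-year rule makes very unlikely to be met at the planned survival rates, and no fallback is given.
- **Interim count.** All power figures above use 174. The conflicting 131 is a separate matter with a larger effect: 74.6% at 348 deaths and about 72% to 73% at 303 to 323.

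**Conclusion.** The concern holds and should be fixed. The stated deaths and power do not follow from the 5-year off-study rule: at the planned survival rates about 303 to 323 deaths are expected instead of 348, and power is about 77% to 79% instead of 80.4%. This rests on exponential survival, no dropout, the stated boundaries with an interim at 174 deaths, and a lag of 0 to 0.5 year to the end of chemoradiation. The direction is secure, because the node-status mixture and loss to follow-up both lower the count further. The exact range depends on the model and on reading section 4.0 as ending survival follow-up for everyone.

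The power loss alone would be minor, and the final level needs no material change. The weight lies in the absent final-analysis trigger and fallback, and in off-study rules that a site cannot apply consistently.

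**What to change.** Reconcile the Follow-Up/Surveillance text of section 4.0 with section 8.0, so that one rule says who leaves at 5 years and whether vital status is still collected. Then choose one of two routes.

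1. **Follow to the event count.** Keep every patient, relapsed or not, under vital-status follow-up by annual contact or record check until a stated trigger of 348 deaths. Add a calendar fallback, with the final boundary recomputed from the spending function at the deaths observed. Only study visits and imaging need end at 5 years. The cost is annual checks, mostly record review of the kind section 8.0 already describes for withdrawals, and a maximum duration of about 8.8 years.
2. **Keep the 5-year limit for all patients.** State a calendar cut-off and restate expected deaths and power for it: about 303 to 323 deaths and 77% to 79% if it waits until the last patient reaches the limit, or about 297 to 311 deaths and 77% to 78% at 8.8 years. The cost is a slightly lower stated power.

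Both are changes of protocol wording, with no added patients, imaging or treatment.
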